## **9 DATA COLLECTION AND PROCESSING**

### **9.1 Data collection**

Subject data will be collected on individual eCRFs and will be substantiated by source documents (such as laboratory reports, medical records or safety ECGs) at the study center. Continuous 12-lead Holter ECG and PK data will be collected electronically and directly via [REDACTED] and [REDACTED], respectively. All relevant data will be transcribed into the eCRF from source documents, entered into the study database directly from source documents or transferred electronically to the study database. Where no printed or electronic source documents exist, data will be entered directly into the eCRF and the eCRF will be considered the source document.

Prior to the start of the study, the Investigator will complete a Delegation of Responsibility List. The Sponsor will provide training for completion of the eCRF. The eCRF will be completed according to guidelines provided by the Sponsor or its designee in writing, electronically and/or verbally.

Completed eCRFs will be reviewed by the study monitor to ensure data accuracy, completeness and consistency. Any discrepancies found during the eCRF review or during data validation and/or quality assurance reviews of the data by data management or other functions are to be clarified by the Investigator (or his/her designated personnel).

The Investigator or designee must record all required subject data using the previously specified data collection method defined by the Sponsor. An explanation must be documented for any missing data. The Investigator must electronically sign and date a declaration on the eCRF attesting to his/her responsibility for the quality of all data recorded, and that the data represents a complete and accurate record of each subject's participation in the study. The data collected in the eCRF will be returned to the Sponsor, and an electronic copy will be retained by the Investigator.

### **9.2 Case Report Form completion**

The eCRF will be presented in an electronic casebook comprising a series of electronic forms. The Subject Number should always be indicated and date (and time, if applicable) of each assessment should be entered in the eCRF.

The eCRFs must be completed in a timely manner so that this does not delay the ongoing data validation, review and quality control. The final, completed eCRF for each subject must be electronically signed and dated by the Investigator on the appropriate eCRF form to signify that he/she has reviewed the electronic casebook and certifies it to be complete and accurate.

### **9.3 Data processing**

The data collected on the eCRFs will be captured in a specially constructed and validated database. The data will be validated using both manual and electronic means. Clarification of data will be requested from the study center as required. An audit trail of the original database entries, changes and deletions, session dates and times and the credentials of the database user who performed the operation will be maintained by the system. The completed database will be quality assured and locked to prevent further changes. A full database extract will be made available for statistical analysis according to the methods outlined in Section 10 and the Statistical Analysis Plan (SAP).

AEs and medical history entries will be coded using the Medical Dictionary for Regulatory Activities (MedDRA). Concomitant medications will be coded using the World Health

Organization Drug Dictionary. Versions of the dictionaries used will be documented in the Data Management Plan and SAP.

## 10 STATISTICAL METHODS AND PLANNED ANALYSES

### 10.1 Determination of sample size

Sample size determination:

The sample size of 27 subjects of IMP per treatments is not based on a formal power calculation. However, referring to the recent publication, even if assuming that is at most 5 msec  $\Delta\Delta QTcF$  in  $C_{max}$  of MCI-186 300 mg as supra-therapeutic dose, 24 subjects of each doses MCI-186 or placebo are considered to be adequate to meet the objectives of the study at power = 80% or higher. In addition, 24 subjects will provide at least 90% power of the upper bound in 90% confidence interval is less than 10 msec, assuming 0 msec  $\Delta\Delta QTcF$  at  $C_{max}$  of MCI-186 60 mg and 300 mg based on simulation using previous studies including MCI-186-E02. Assuming a few drop-out, a total of 27 subjects are planned to be randomized in this study.

### 10.2 Interim and Final Reporting

The study will have a final database lock. The final database lock will occur when all outstanding data queries have been resolved and the database is fully cleaned. This data will then be used to produce a full set of unblinded tables, figures and listings for the Clinical Study Report. The tables, figures and listings will then be communicated to the wider study team.

### 10.3 Study populations

The statistical analysis will be based on the following defined populations:

- Safety population includes all randomized subjects who received at least one dose of IMP.
- PK population includes all randomized subjects who received at least one dose of IMP and who have at least one post-dose value of plasma concentration without important Protocol deviations which may affect the PK of the IMP.
- PD population includes all randomized subjects who received at least one dose of IMP and who have at least one PD 12-lead ECG extracted post-dose.

The safety population will be used for all safety summaries. PK assessments will be performed on the PK population and PD assessments will be performed on the PD population.

### 10.4 Statistical analysis

#### 10.4.1 General considerations

All individual subject data will be listed.

The statistical analysis will be performed using SAS® Version 9.2 or higher.

All variables will be summarized by treatment.

Unless otherwise stated, continuous data will be summarized descriptively including: number of subjects (N), number of observations (n), mean, standard deviation (SD), minimum, median and maximum. Categorical data will be summarized using frequency tables (frequency and percent).

The PK concentrations will be summarized by planned sampling time.

A detailed SAP will be prepared and approved prior to the study database lock which will include all detailed data handling and statistical methods. Any deviations from the planned analyses will be described and justified in the final integrated Clinical Study Report.

#### 10.4.2 Missing Data handling

Procedures for the handling of any missing data will be described in the SAP.

#### 10.4.3 Analysis of demography and other baseline subject characteristics

The number of subjects screened, randomized and included in each analysis population will be provided.

Demographic data and baseline characteristics such as age, ethnicity/race, height, body weight, BMI, smoking and alcohol use will be summarised. No formal statistical analysis of demographic or baseline characteristics will be performed.

Medical history will be coded using MedDRA latest version and listed for all subjects.

#### 10.4.4 Pharmacodynamic ECGs

All interval values analysed will be the mean of the up to three replicate ECGs at each timepoint. Correction of QT for HR will be performed on each individual ECG prior to averaging using the Fridericia method:

$$QTcF = QT/RR^{(1/3)} \text{ (with RR expressed in units of seconds).}$$

#### 10.4.5 Analysis of primary endpoint – PD ECGs Continuous 12-lead Holter extracted PD electrocardiogram

Data from continuous 12-lead Holter monitoring based on the extracted PD ECGs will be analyzed to investigate the potential effect of MCI-186 on the QTc interval.

Concentration-response analysis:

The primary outcome measure will be an analysis of the regression relationship between  $\Delta QTcF$  and the plasma concentration of MCI-186 at matching times postdose, including adjustment for placebo subjects, for the combined dose groups, as follows:

- A linear mixed effects model with  $\Delta QTcF$  as the dependent variable, the intercept, slope, influence of baseline on intercept, treatment (MCI-186=1 or placebo=0) and time from first administration as fixed effect parameters, intercept and slope as additive random effects in below.

$$\begin{aligned} \Delta QTc_{i,j,k} = & \theta_0 + \eta_{0,i} + \theta_1 TRT_j + (\theta_2 + \eta_{2,i}) C_{i,j,k} + \theta_3 TIME_j \\ & + \theta_4 (QTc_{i,j,k=0} - \overline{QTc}_0) \end{aligned}$$

*Note:*

$\Delta QTc_{i,j,k}$  : the change from baseline in QTc for subject  $i$  in treatment  $j$  at time  $k$

$\theta_0$  : the population mean intercept in the absence of a treatment effect

$\eta_{0,i}$  : the random effect associated with the intercept term  $\theta_0$

$\theta_1$  : the fixed effect associated with treatment  $TRT_j$  (0=placebo, 1=MCI-186)

$\theta_2$  : the population mean slope of the assumed linear association between concentration and  $\Delta QTc_{i,j,k}$

$\theta_3$  : the fixed effect associated with time

$\eta_{2,i}$  : the random effect associated with the slope term  $\theta_2$

$C_{i,j,k}$  : the concentration for subject  $i$  in treatment  $j$  at time  $k$

$\theta_4$  : the fixed effect associated with baseline  $QTc_{i,j,k=0}$

$\overline{QTc}_0$  : the overall mean of all the baseline (=time 0)  $QTc_{i,j,k=0}$  values

It is assumed the random effects are bivariate normally distributed with mean [0,0] and an unstructured covariance matrix  $G$ , whereas the residuals are normally distributed with mean 0 and  $R$

- Point estimates for between-group difference in each MCI-186 group and combined placebo groups ( $\Delta\Delta QTcF$ ) and corresponding 2-sided 90% CI will be constructed at the geometric mean  $C_{max}$  of each dose level of MCI-186, and for the quintiles of overall MCI-186 concentration.

It will be concluded that no significant repolarization effect was detected if the upper 90% CI of  $\Delta\Delta QTcF$  are <10 msec at the geometric mean  $C_{max}$  for both dose levels of MCI-186.

#### **10.4.6 Analysis of secondary PD ECG endpoints**

##### **10.4.6.1 ECG interval analysis:**

Absolute value and change from baseline will be summarized by descriptive statistics (N, n, mean, SD, median, minimum and maximum) for HR, PR interval, QRS interval, and QTcF intervals at each time point by each treatment.

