	
supplements, except for acetylsalicylic acid, within 7 days prior to IMPs dosing.
 
16. Use of tobacco or nicotine containing products for 24 hours before each visit of screening or Day -1.
 
17. Consumption of alcohol, xanthines, or grapefruit containing products for 24 hours before each visit of screening or Day -1.

Triplicate ECG and PK Sampling	
Continuous 12-lead Holter monitoring will be performed from at least 1 hour prior until 24 hours after dosing. From the Holter data, triplicate 12-lead pharmacodynamic (PD) ECGs of 10-seconds duration will be extracted at the following timepoints in relation to start of infusion: -45, -30 and -15 min; and 30, 60, 75, 90, and 105 min, and 2, 3, 4, 6, 8, 12 and 24 hours. PK samples for concentration of MCI-186 will be obtained predose, and after each of the ECG timepoints that occur after start of dosing.

Endpoints:	
Primary Endpoint:
 
 
Relationship of change from baseline in QTcF (<math>\Delta QTcF</math>) with placebo adjustment (<math>\Delta\Delta QTcF</math>) and concentration of MCI-186
 
 
Secondary Endpoints:
 
 
Assessment of heart rate (HR), PR interval, QRS interval, and QTcF by timepoint
 
Categorical outliers for QTcF interval (absolute value and change from baseline) and other ECG parameters (if necessary)
 
Incidence of abnormalities in ECG morphology
 
PK parameters of MCI-186
 
Incidence of adverse events (AEs) and serious adverse events (SAEs), vital signs, safety 12-lead ECG variables, laboratory tests and physical examination
 

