#### **2.1.2 Secondary objectives**

- To evaluate the PK profile of MCI-186
- To evaluate the effect of MCI-186 on other 12-lead ECG intervals
- To evaluate the safety and tolerability of MCI-186

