#### **2.1.4 Secondary endpoints**

- Assessment of HR, PR interval, QRS interval, and QTcF by timepoint
- Categorical outliers for QTcF interval (absolute value and change from baseline) and other 12-lead ECG parameters
- Incidence of abnormalities in ECG morphology
- PK parameters of MCI-186
- Incidence of adverse events (AEs) and serious adverse events (SAEs), vital signs, safety 12-lead ECG variables, laboratory tests and physical examination

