### **7.4 Maintenance of the study blind and unblinding**

This study is a single-blind study. Subjects and ECG reviewer will be blinded. Investigator and Sponsor will be unblinded.

Treatment during all study parts will be single-blind, that is, the subject and ECG reviewer will not know which treatment is being infused (MCI-186 or placebo). The subject's I.V. delivery containers will be labelled with a unique number, which is traceable to the subject and treatments.

For each subject, randomization lists will be held in a secure area by the responsible person for allocation of IMP. If the blind is broken for any individual subject by the Investigator, the subject must be withdrawn from the study, and any procedures accompanying withdrawal should be performed (Section 4.5). The procedure for randomization and blinding in this study will be prepared by the responsible person for allocation of IMP and randomization of treatment sequence.

Due to PK analysis only being performed on samples from subjects receiving active IMP (MCI-186), the unblended Randomization list will be held by Bioanalytical Laboratory. (who will not have any influence on the clinical conduct of the study).

The Sponsor will authorise release of the unblinded Randomization list at the end of the study.

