##### **10.4.6.2 Categorical analysis:**

Categorical analysis will be performed to summarize the number and percentage of subjects meeting each criterion on each treatment.

Absolute QTcF interval prolongation:

- QTcF interval >450 msec
- QTcF interval >480 msec
- QTcF interval >500 msec

Change from baseline in QTcF interval:

- QTcF interval increases from baseline >30 msec
- QTcF interval increases from baseline >60 msec

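### HR, PR and QRS receive only by-treatment descriptives; neither the protocol nor the supplied SAP plans a within-subject comparison with placebo for this secondary objective

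*Protocol*

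**What the plan says.** - **Objective.** Protocol 2.1.2: "To evaluate the effect of MCI-186 on other 12-lead ECG intervals".
- **Endpoints.** Protocol 2.1.4 lists "Assessment of HR, PR interval, QRS interval, and QTcF by timepoint" and "Categorical outliers for QTcF interval (absolute value and change from baseline) and other 12-lead ECG parameters". The synopsis words the last part as "other ECG parameters (if necessary", which makes it conditional.
- **Interval analysis.** Protocol 10.4.6.1: "Absolute value and change from baseline will be summarized by descriptive statistics". The statistics are N, n, mean, SD, median, minimum and maximum, for HR, PR, QRS and QTcF, at each time point by treatment. No contrast and no interval is mentioned.
- **Outlier analysis.** Protocol 10.4.6.2: "Categorical analysis will be performed to summarize the number and percentage of subjects meeting each criterion on each treatment". Every criterion listed there is for QTcF.
- **Placebo adjustment.** Protocol 10.4.5 plans a placebo-adjusted estimate with a 2-sided 90% CI, for QTcF only.
- **QT correction.** Protocol 3.7 relies on no HR effect being expected.
- **SAP.** Section 1 refers Holter ECG analysis to a separate ECG SAP. Sections 5.5, 7.7.1 and 7.7.5 rule out testing and estimation in the supplied SAP. Section 7.9.4 describes the bedside safety ECGs, with cut-offs for QTcF only. The revision history (section 13) says that 2.1.1, 2.1.3 and 2.1.4 were underlined as not planned in this SAP. It does not list 2.1.2.

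**The concern.** An effect of the drug is a difference from placebo. QTcF has the primary model for that. In the supplied documents HR, PR and QRS have only separate summaries per treatment. Those summaries do not contain the SD of the within-subject differences, so they do not use the pairing that a three-way crossover provides.

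HR carries the most weight. The choice of QTcF as the primary measure rests on HR not moving, and no analysis stated in these documents estimates HR change against placebo with an interval. A large shift would show in the table of means. A modest one, or its absence, would be reported without a planned measure of precision.

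A smaller matter is the outlier endpoint. Section 2.1.4 promises outliers for other parameters, the synopsis makes them conditional without a trigger, and 10.4.6.2 gives no limits for them.

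**Working it through.** **1. The plan's own figures.** Protocol 10.1 gives power for 24 evaluable subjects out of 27 randomized, for QTcF only. No SD, correlation or precision target is given for HR, PR or QRS, so there is no figure to reproduce here.

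**2. Inputs.** From the documents: n = 27 randomized, 24 expected to be evaluable (10.1); 12 post-dose ECG times (6.4: 30, 60, 75, 90 and 105 min; 2, 3, 4, 6, 8, 12 and 24 h); two active doses. Assumed, because the documents are silent: equal SD of change on each treatment, 4 to 10 units (8 msec for PR as the worked case), and between-period correlation ρ of 0.3 to 0.7.

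**3. What the planned tables allow.** In subjects who complete all periods, mean(drug) − mean(placebo) equals the mean of the within-subject differences, so the point estimate can be recovered. Its variance cannot:

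- Unpaired SE = SD·√(2/n), from the by-treatment SDs.
- Paired SE = SD·√(2(1−ρ)/n), which needs ρ or the SD of differences.
- Ratio = √(1−ρ): 0.837 at ρ = 0.3, 0.707 at 0.5, 0.548 at 0.7.

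**4. Worked case, SD = 8, n = 27.**

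- Unpaired: SE = 8 × √(2/27) = 8 × 0.272 = 2.18; t(0.95, 52) = 1.675; 90% half-width 3.65.
- Paired, ρ = 0.5: SE = 8 × √(1/27) = 8 × 0.1925 = 1.54; t(0.95, 26) = 1.706; half-width 2.63.
- Paired, ρ = 0.3: half-width 3.11. Paired, ρ = 0.7: half-width 2.03.
- Ratios of half-widths: 3.11/3.65 = 0.852, 2.63/3.65 = 0.721, 2.03/3.65 = 0.556. The interval is about 15%, 28% and 44% narrower. These reductions are slightly smaller than the SE ratios imply, because the paired t has fewer degrees of freedom.

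**5. Range of 90% half-widths.**

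| n | Assumed SD | Unpaired | Paired, ρ = 0.3 | Paired, ρ = 0.7 |
|---|---|---|---|---|
| 27 | 4 | 1.82 | 1.55 | 1.02 |
| 27 | 10 | 4.56 | 3.88 | 2.54 |
| 24 | 4 | 1.94 | 1.66 | 1.08 |
| 24 | 10 | 4.85 | 4.14 | 2.71 |

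The relative gain is almost the same at n = 24 and does not depend on the SD. At ρ = 0 there is none: with SD 8 and n = 27 the paired half-width is 3.71 against 3.65. The paired t stands in for the mixed model proposed below; the model's degrees of freedom will differ somewhat.

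**6. Number of new intervals.** 12 times × 2 doses × 3 parameters = 72. With no effect anywhere, about 10%, or 7, of the 90% intervals would exclude zero by chance.

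**The case against.** The strongest objection is that the Holter analysis belongs to an ECG SAP that is not available here. Protocol 10.4.1 also leaves detailed methods to a SAP approved before database lock. This stands: absence can be asserted only for the protocol and the supplied SAP. A reader might infer that the trial has no drug-placebo comparison for these intervals at all, and the documents do not support that.

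A reader might also infer that no effect, or no uncertainty, could be stated for HR, PR or QRS. That goes too far. The crude difference comes straight from the planned means, an unpaired CI from the SDs and n is wider than needed over the assumed range of ρ, and 10.4.1 provides for listing all individual data, so paired differences could be computed later. What is missing is a planned, adjusted contrast; one built from listings would be post hoc.

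Descriptive reporting of secondary intervals is a legitimate choice. No margin or decision rule is attached to them. That limits the weight of the point, but the stated objective is an effect and the better estimate needs no new data.

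On outliers, a reader might infer that the Sponsor can freely pick what to report, since "Investigator and Sponsor will be unblinded" (7.4). The discretion is real but limited: the ECG reviewer is blinded, a SAP must be approved before lock, deviations must be justified, and 10.4.6.1 already commits to minimum and maximum values for each parameter. This part is a wording conflict, not an analysis error.

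**Conclusion.** The point holds as a worthwhile, inexpensive improvement. In the protocol and supplied SAP, the secondary objective on other ECG intervals is served by unpaired by-treatment summaries although the design is paired. The cost is precision and a missing pre-planned estimate: a 90% CI built from the tables would be wider than a paired one, which would be about 15% to 44% narrower at n = 27. That size rests on an assumed ρ of 0.3 to 0.7 and equal SDs; a lower ρ would shrink it. HR is the parameter where the gap matters most, because of section 3.7.

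Whether the gap exists in the trial's full set of plans depends on the ECG SAP. Which plan covers this objective is not fully clear either, because 2.1.2 is not among the sections recorded as underlined. The outlier wording is secondary.

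**What to change.** 1. In Protocol 10.4.6.1, and in the ECG SAP unless it already does so, add a crossover mixed model for change from baseline in HR, PR and QRS. Include treatment (60 mg, 300 mg, placebo), nominal time, treatment-by-time, period, sequence and baseline as fixed effects and subject as a random effect, and allow for within-subject correlation across times.
2. Report the LS-mean difference from placebo with a 2-sided 90% CI for each dose and time point. Present it as estimation only, with no decision rule, labelled as unadjusted for multiplicity.
3. If the ECG SAP already contains this, cross-refer to it from 10.4.6.1 and state that it covers the other-intervals objective in 2.1.2.
4. Reconcile the unconditional outlier endpoint in 2.1.4 ("and other 12-lead ECG parameters") with the conditional synopsis wording and the QTcF-only criteria in 10.4.6.2. If other-parameter outliers are kept, the sponsor should fix the parameters and limits before treatment-level data are reviewed. The PR and QRS limits in exclusion criterion 1 are entry limits, and the documents do not present them as on-treatment outlier limits.

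The cost is wording and a few tables from data already collected. The downside is about 72 more descriptive intervals, some of which will exclude zero by chance, so the label in item 2 matters.

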##### **10.4.6.2 Categorical analysis:**

Categorical analysis will be performed to summarize the number and percentage of subjects meeting each criterion on each treatment.

Absolute QTcF interval prolongation:

- QTcF interval >450 msec
- QTcF interval >480 msec
- QTcF interval >500 msec

Change from baseline in QTcF interval:

- QTcF interval increases from baseline >30 msec
- QTcF interval increases from baseline >60 msec

##### **10.4.6.3 Morphological analysis:**

Morphological analysis will be performed to summarize the number and percentage of subjects in each treatment having the appearance of a morphological abnormality not present at baseline.

#### **10.4.7 Plasma concentration of unchanged MCI-186**

Plasma concentration-time profiles of unchanged MCI-186 for each subject and mean plasma concentration-time profiles will be plotted, plasma concentration data at each time point will be summarized by descriptive statistics, and PK parameters will be summarized with mean, median, geometric mean, minimum, maximum, standard deviation, and coefficient of variation.

